# 3.5.2.5 Annualized Flare Rate for AC-Determined IgG4-RD Flares, Whether or not Treated, During the RCP

The estimand with a treatment policy strategy is defined by the following:

- Target population: Subjects in the FAS
- Variable: The number of AC-determined IgG4-RD flares, whether or not treated, experienced during 52-week RCP
- Intercurrent event: No intercurrent events will be taken into account. All data captured during the 52-week RCP will be used for analysis.
- Population-level summary: Rate ratio between inebilizumab versus placebo and its associated 95% CI.

The number of treated AC-determined flares will be compared between the inebilizumab group and the placebo group using a negative binomial model. The model will include covariates of treatment group (inebilizumab or placebo) and stratification factors. The logarithm of the subject's corresponding follow-up time will be used as an offset variable in the model to adjust for subjects having different exposure times during which the events occur. The estimated treatment effect (ie, the rate ratio of inebilizumab versus placebo), corresponding 95% CI, and two-sided p-value for the rate ratio will be presented.

In addition, the annualized flare rate and the corresponding 95% CI within each treatment group, and the absolute difference between treatment groups with the corresponding 95% CI, will be presented.

#### 3.5.2.6 Glucocorticoid Use

The estimand is defined by the following:

- Target population: Subjects in the FAS
- Variable: Cumulative GC dose taken for the purpose of disease control during the 52week RCP
- Intercurrent event: All data captured during the 52-week RCP will be used for analysis. GC use for a purpose other than controlling IgG4-RD or for protocol-specified steroid tapering will not be included in the analysis.
- Population-level summary: Difference in means GC dose between inebilizumab versus placebo and its associated 95% CI.

Total GC use per subject and daily GC use per subject will be summarized and analyzed by analysis of covariance models with treatment indicator (inebilizumab or placebo) and stratification factor as the explanatory variables. Results will be presented in terms of least square means (LSMEANS), treatment differences in LSMEANS, 95% Cis, and p-values.

#### 3.5.3 Subgroup Analyses

Consistency of treatment effect measured by primary and 3 key secondary endpoints in the following subgroups will be investigated:

- Age (< 65 vs  $\ge$  65)
- Sex (male vs female)
- Region (US vs non-US; EU vs non-EU; and Asia vs non-Asia)
- Serum IgG4 concentrations at baseline (< median vs  $\ge$  median)
- Racial/ethnic subgroups as needed for national/regional regulatory filings
- First or subsequent IgG4-RD manifestation (i.e., newly diagnosed vs. recurrent)
- Anti-drug antibody (ADA) status at any time during RCP including baseline (positive vs. negative) if data allows

The nominal p-value and 95% Cis of treatment effect will be provided for each subgroup analysis. Forest plots will be generated to visually present the consistency of treatment effect in different subgroups with overall treatment effect. Interaction tests would be conducted to evaluate the consistency of the treatment effect among the different categories of each subgroup variable.

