2.1.5.5 Immunogenicity

In Study MI-CP200, ADA to inebilizumab were detected in 4/24 subjects (16.7%) treated with inebilizumab (1 each in 0.3, 1.0, 3.0, and 10.0 mg/kg dose cohort). None of the subjects treated with placebo (N = 4) tested positive for the presence of ADA at any time throughout the study.

Clinical Study Protocol	Horizon Therapeutics Ireland DAC
VIB0551.P3.S2 - MITIGATE	Inebilizumab
Amendment 9.1, 08AUG2023	IgG4-Related Disease

No apparent impact on B-cell depletion was observed in ADA-positive subjects following a single dose of inebilizumab.

In Study 1102, none of the 28 subjects in the study (21 inebilizumab-treated and 7 placebo) tested positive for the presence of ADA.

In the RCP of Study 1155, the prevalence of ADA-positive subjects (ADA positive at baseline or at any time during the RCP) was 9.8% of the inebilizumab group and 14.3% of the placebo group. Treatment-emergent ADA (post-baseline positive only) were observed in 2.9% and 7.1% of inebilizumab and placebo-treated subjects, respectively. Overall, there was no marked difference in the mean PK profiles of inebilizumab in ADA-positive and ADA-negative subjects. Additionally, there was no apparent effect of ADA on the efficacy of inebilizumab.

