#### 3.8 Immunogenicity

The ADA analysis will be based on the Safety Analysis Set. The ADA status in Table 9Error! Reference source not found. will be summarized by the categories included in the table and the ADA titer may be summarized for ADA positive subjects. The impact of ADA on safety may be evaluated if needed.

ADA Status	Definition
Prevalence (Positive during the study)	ADA positive observed at least once during the study (baseline included)
Incidence (treatment emergent ADA)	ADA positive post-baseline only or boosted their pre-existing
	ADA titer ( $\geq$ 4-fold increase) during the study period
Negative during the study	ADA positive not observed at any visit during the study (baseline included)
Baseline positive	ADA positive observed at baseline regardless of the post- baseline ADA status
Post-baseline positive	ADA positive observed at least once during post-baseline regardless of the baseline ADA status
Only baseline positive	ADA positive observed at baseline but not observed at any time post-baseline
Only post-baseline positive (treatment-induced)	ADA positive not observed at baseline but observed at least once post-baseline
Both baseline and post-baseline positive	ADA positive observed at baseline and observed at least once post-baseline

Table 9 Definition	of ADA Status
---------------------------	---------------

Persistent positive	Treatment-induced ADA positive at $\geq 2$ post-baseline assessments (with $\geq 16$ weeks between first and last positive) or positive at last post-baseline assessment
Transient positive	Treatment-induced ADA post-baseline positive but does not fulfil the criteria of persistent positive

ADA = anti-drug antibodies.

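### The ADA efficacy subgroup is set partly by post-dose results, so its between-arm comparison and interaction test are not fully randomised comparisons

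*SAP*

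**What the plan says.** SAP 3.5.3 states that "Consistency of treatment effect measured by primary and 3 key secondary endpoints in the following subgroups will be investigated". The list covers age, sex, region, baseline serum IgG4, racial or ethnic group, disease manifestation (newly diagnosed or recurrent) and, last, "Anti-drug antibody (ADA) status at any time during RCP including baseline (positive vs. negative) if data allows".

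For all of these, "The nominal p-value and 95% Cis of treatment effect will be provided for each subgroup analysis", forest plots are drawn, and "Interaction tests would be conducted to evaluate the consistency of the treatment effect among the different categories of each subgroup variable". ADA gets no separate treatment and no caveat.

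Other relevant places:
- **SAP 3.8, Table 9** already defines a baseline-only category, baseline positive: "ADA positive observed at baseline regardless of the post- baseline ADA status". It also has a separate category for subjects positive only after baseline. SAP 3.5.3 uses neither.
- **SAP 3.6.1**, after Table 6, uses the same any-time ADA variable for adverse-event subgroups.
- **Protocol 9.5.4** does not list ADA among the efficacy subgroups. Protocol 9.5.7 says only that the effect of ADA on safety and efficacy may be explored if the data permit.
- **Protocol Table 4** has an ADA row that is broken in the extracted text. It reads as Weeks 0, 4, 12, 26, 38 and 52, so five of the six samples follow the first dose.

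**The concern.** Every other subgroup in the list is fixed before dosing, so randomisation protects the comparison inside each level. ADA status is the one variable that post-dose data can set, and that protection is lost for the post-dose part in three ways.

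1. **Treatment.** A placebo subject has no inebilizumab exposure in the controlled period, so a post-baseline positive result there cannot be a response to the drug. On inebilizumab it can be.
2. **Follow-up.** A subject who leaves early gives fewer samples and has fewer chances to be classed as positive.
3. **Order in time.** A subject can first test positive after the flare. Under Protocol 7.5.1 and 7.6, some flare treatments also require investigational product to be stopped, so the outcome can change later drug exposure.

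At stake is one line of a forest plot and its interaction p-value. They would stand beside true baseline subgroups and could be read as showing that ADA does, or does not, change efficacy.

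**Working it through.** **Planning figures reproduced (SAP 2.3).** HR 0.35, two-sided alpha 0.05, 90% power, 1:1 allocation. Events = 4(1.960 + 1.282)² / (ln 0.35)² = 38.1, so 39. Placebo flare probability is 0.35. Inebilizumab: 1 − exp(−0.1508) = 0.140. Average 0.245; 39/0.245 = 159, in line with 160. The plan's own figures hold.

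**ADA rates (Protocol 2.1.5.5, Study 1155).** Prevalence at baseline or any time in the controlled period "was 9.8% of the inebilizumab group and 14.3% of the placebo group". Positive only after baseline: 2.9% and 7.1%. By subtraction, positive at baseline: 9.8 − 2.9 = 6.9% and 14.3 − 7.1 = 7.2%. Baseline positivity was thus nearly equal, and almost all of the arm difference arose after baseline. Post-baseline-only subjects were 2.9/9.8 = 30% of positives on inebilizumab and 7.1/14.3 = 50% on placebo.

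**Precision, projected to 80 per arm.** SE of the log ratio of hazard ratios = square root of the summed reciprocals of expected flares in the four cells.

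| Quantity | Any-time ADA (SAP) | Baseline ADA |
|---|---|---|
| Positives, inebilizumab + placebo | 7.84 + 11.44 = 19.3 | 5.52 + 5.76 = 11.3 |
| Flares in positives | 1.10 + 4.00 = 5.1 | 0.77 + 2.02 = 2.8 |
| Flares in negatives | 10.10 and 24.00 | 10.42 and 25.98 |
| Sum of reciprocals | 0.911 + 0.250 + 0.099 + 0.042 = 1.302 | 1.294 + 0.496 + 0.096 + 0.038 = 1.925 |
| SE | 1.14 | 1.39 |
| Ratio of HRs needed for p < 0.05, exp(1.96 × SE) | about 9 | about 15 |

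This table measures imprecision. It says nothing about bias.

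**Whether selection alone can separate the two hazard ratios.** This is an illustration under assumed inputs, not an estimate. Take two equal risk classes with a fourfold hazard ratio between them and a placebo flare probability of 0.35 overall. The class hazards are then 0.188 and 0.752. Every subject has the same treatment HR of 0.35. Baseline ADA is 7% in both classes, and post-baseline ADA averages 2.9% and 7.1% as in Study 1155.

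- *Case A.* Post-baseline ADA is three times as likely in the high-risk class on inebilizumab and one third as likely on placebo.
  - Inebilizumab: positivity is 8.45% (low risk) and 11.35% (high risk); flare probability among positives = (0.0845 × 0.0637 + 0.1135 × 0.2314)/0.198 = 0.160.
  - Placebo: 17.65% and 10.55%; (0.1765 × 0.1714 + 0.1055 × 0.5286)/0.282 = 0.305.
  - Ratio of cumulative hazards = 0.174/0.364 = 0.48. The same calculation in ADA-negatives gives 0.36.
- *Case B.* No dependence on risk on inebilizumab, three times as likely in high-risk placebo subjects. The ratio is 0.32 in positives and 0.38 in negatives.
- *Baseline ADA only.* The ratio is 0.37 in both groups. It differs from 0.35 only because two risk classes are mixed.

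The same true effect can therefore appear weaker or stronger in ADA-positives, depending on inputs that the documents do not give.

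**The case against.** The strongest case on the other side has five parts.

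- **The classifier is mixed.** On Study 1155 rates, about 70% of inebilizumab positives (6.9/9.8) and 50% of placebo positives (7.2/14.3) were already positive at baseline. This stands. A reader might infer that the subgroup is purely a post-randomisation outcome, or that any interaction would be purely selection; the documents do not support either.
- **The analysis is already limited.** It runs only if the data allow, its p-values are nominal, and SAP section 5 leaves it outside the controlled family. This stands, and it limits the consequence. It does not cure the comparison: more data would narrow the interval around the same contrast.
- **Evidence that treatment drives ADA is thin.** Two subjects being 3.6% implies about 56 on placebo, so about 230 − 56 = 174 on inebilizumab. Post-baseline-only positives are then about 5/174 against 4/56 (Fisher p about 0.23), and the rate is higher on placebo. This stands as a reason not to claim a direction. The objection to the method does not need one.
- **Follow-up is designed to be complete.** ADA visits are fixed, and subjects who flare or stop product are to stay through Week 52. This reduces unequal sampling but does not address treatment-induced ADA or ADA detected after the flare.
- **Baseline ADA is less precise.** True: SE 1.39 against 1.14. That is the price of a comparison that randomisation supports.

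A reader might also take the ninefold ratio as the size of the bias. It is not. If anything, it means a false significant interaction would be rare and a non-significant one uninformative.

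**Conclusion.** The point holds as a minor one. As written, SAP 3.5.3 yields an ADA comparison that is only partly protected by randomisation and shows it alongside subgroups that are fully protected. Apparent interaction or consistency could reflect selection, and the documents do not allow its direction or size to be derived.

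No primary or key secondary conclusion depends on it. The projection of about 19 positives, 5 flares and an SE of 1.14 assumes that Study 1155 rates carry over from neuromyelitis optica spectrum disorder and a 28-week period to this 52-week trial, with the planned flare probabilities and 80 subjects per arm.

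**What to change.** - **SAP 3.5.3:** define the between-arm ADA subgroup and its interaction test by baseline status, using the baseline-positive category of Table 9. Keep the condition that the data allow it.
- **Post-baseline ADA:** describe flares by post-baseline ADA within the inebilizumab arm only, giving the date of first positive ADA relative to the flare, with no between-arm hazard ratio and no interaction p-value. On Study 1155 rates this is about 2 subjects (2.9% × 80), so a listing may be enough. The timing matters because a within-arm split by later ADA status otherwise keeps the order-in-time problem.
- **SAP 3.6.1:** make the same change, or add the same caveat, for the adverse-event subgroups by any-time ADA.

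The cost is SAP wording, with no new data collection. The downside is lower precision in an already small subgroup: about 11 subjects and 3 flares in place of 19 and 5.

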#### **3.5.4 Exploratory Efficacy Endpoints and Analyses**

#### 3.6 Safety Analysis

Safety endpoints will be summarized separately for the RCP, OLP, SFP, and combined RCP and OLP. Safety data from the RCP and OLP will be presented based on the Safety Analysis Set and on the Open-label Analysis Set, respectively. Safety data from the combined RCP and OLP will be analyzed based on the Any Inebilizumab Analysis Set.

#### **3.6.1** Adverse Events

Adverse event and serious adverse event collection begins after the subject signs the informed consent document and continues until the end of study visit. AEs and SAEs collected during the RCP will be analyzed using a treatment policy strategy (which includes all data captured during the RCP), and a while-on-treatment strategy (which includes all data captured while subjects are on treatment). AEs and SAEs collected during the OLP, SFP and combined RCP and OLP, will be analyzed using a treatment policy strategy. For subjects who withdraw from the study, data collected up until the last visit will be included. Table 5 defines TEAEs for different analyses.

RCP (Treatment Policy)	RCP (While-on- treatment)	OLP	Combined RCP and OLP (Any Inebilizumab Analysis Set)	SFP
A TEAE is defined as any AE with onset date on or after the first RCP IP dose, and on or before the end of RCP.	A TEAE is defined as any AE with onset date on or after the first RCP IP dose, and on or before 6 months (183 Days) after the last RCP dose.	A TEAE is defined as any AE with onset date on or after first OLP IP dose and up to the end of OLP (prior to the SFP entry if a subject enrolled into SFP).	A TEAE is defined as any AE with onset date on or after the first inebilizumab dose (either RCP or OLP) and up to and including the day prior to the end of RCP (if a subject didn't enroll into OLP) or the end of OLP (i.e., the day prior to the SFP entry, if a subject rolled over to OLP).	TEAE is defined as any AE with onset date after the last IP dose during the study.

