 - A causal relationship between the IP and the event is biologically implausible (eg, death as a passenger in an automobile accident)
 - A clearly more likely alternative explanation for the event is present (eg, typical adverse reaction to a concomitant drug and/or typical disease-related event)

Individual AE/SAE reports will be considered "related" to use of the IP if the "not related" criteria are not met.

"Related" implies that the event is considered to be "associated with the use of the drug" meaning that there is "a reasonable possibility" that the event may have been caused by the IP (ie, there are facts, evidence, or arguments to suggest possible causation).

- Adverse reaction An adverse reaction is any AE caused by a drug.
- Suspected adverse reaction A SAR is any AE for which there is a reasonable possibility that the drug caused the AE. For the purposes of safety reporting to regulatory agencies, "reasonable possibility" means there is evidence to suggest a causal relationship between the drug and the AE. SAR implies a lesser degree of certainty about causality than an adverse reaction.
- Unexpected An event is considered unexpected if it is not listed in the IB, is not listed at the specificity or severity that has been observed, or, if an IB is not required or available, is not consistent with the risk information described in the General Investigational Plan or elsewhere. Unexpected also refers to events that are mentioned in the IB as occurring with a class of drugs or as anticipated from the pharmacological properties of the drug but are not specifically mentioned as occurring with the particular IP.
- Severity or intensity Severity will be graded according to the CTCAE, version 5.0. The determination of severity for events not listed in the CTCAE should be made by the Investigator based upon medical judgment and the severity categories of Grade 1 to Grade 5 as defined here, with the maximum severity recorded:
 - Grade 1 (mild): An event of mild intensity that is usually transient and may require only minimal treatment or therapeutic intervention. The event does not generally interfere with usual activities of daily living.
 - Grade 2 (moderate): An event of moderate intensity that is usually alleviated with additional, specific therapeutic intervention. The event interferes with usual activities of daily living, causing discomfort but poses no significant or permanent risk of harm to the subject.

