8.3 Reporting Adverse Events

All AEs (related and unrelated) will be recorded from written ICF signature up to exit from the study, whether or not related to the study.

In addition to eCRF entry, all SAEs must be reported to the Sponsor within 24 hours of site staff awareness by submitting a SAE Report Form by email to:

Email: [contact]

Alternatively, the SAE Report Form can be submitted by fax to:

US-Only [contact]

EX-US [contact]

Additional follow-up information, if required or available, should all be reported within one business day of receipt, should be completed on a follow-up SAE form, placed with the original SAE information, and kept with the appropriate section of the eCRF and/or study file.

The Sponsor will work with the Investigator to ensure that all the necessary information is provided within one calendar day of initial receipt for fatal and life threatening events and within 5 calendar days of initial receipt for all other SAEs.

Sponsor or designee is responsible for notifying the relevant regulatory authorities of certain events. Notification of the IRB or IEC of all SAEs that occur at the Investigator's site are the responsibility of the Investigator. Investigators will be notified of all unexpected, serious, drug -related events (7 and 15 Day Safety Reports) that occur at other investigative sites during the clinical trial. Each Investigator is responsible for notifying its IRB or IEC of these additional SAEs.

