#### **Table 5 Definition of TEAEs for Different Analyses**

An adverse event of special interest (AESI) is one of scientific and/or medical interest specific to understanding safety and action of the IP. The following are considered AESIs in this study:

- Anaphylaxis and serious hypersensitivity reactions
- Infusion-related reactions (IRR)
- Immune complex disease
- Cytopenia
- Serious and/or opportunistic infections, including Progressive Multifocal Leukoencephalopathy (PML).

The AESIs (investigator reported) will be summarized by Category and PT. The risk difference and corresponding 95% CI calculated by the Miettinen and Nurminen score method in cumulative incidences of AESIs by week 52 between inebilizumab and placebo groups may be presented as appropriate. In addition, the time to first instance of an AESI and duration of the AESI will be summarized by treatment group when appropriate.

In addition, following sponsor identified AESIs will also be summarized: IRR, anaphylaxis, serious hypersensitivity reactions, immune complex disease, cytopenia, serious infections, and opportunistic infections. The detailed definition of sponsor identified AESIs will be included in the statistical programming plan (SPP).

AEs will be coded to the corresponding system organ class (SOC) and preferred terms (PT) using the most recent version of the Medical Dictionary for Regulatory Activities (MedDRA). In addition, summary of AEs and SAEs by SOC and FDA Medical Query (FMQ) will also be provided for RCP and the combined period of RCP and OLP.

The number and percentage of subjects reporting TEAEs and TESAEs will be summarized for each treatment group by SOC and PT, by severity, and by relationship to the IP. If the same AE occurs multiple times within a particular subject, the highest severity and level of relationship observed will be reported.

TEAEs and TESAEs will be summarized as described in Table 6.

TEAEs per 100 Person-years for a specific reporting period will be calculated as

$$= 100 \times \frac{\text{Total number of TEAEs for specific reporting period}}{\text{Total Person years for specific reporting period}}$$

The person-year for while-on-treatment analyses will be defined as (Date of 6 months [183 Days] after the last RCP dose - 1st RCP dose date +1)/365.25. See Table 4 for the definition of person-years for other analyses.

Overall summary of TEAEs
TEAEs by SOC and PT
TEAEs with severity $\geq$ Grade 3 by SOC and PT

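### SAP Table 5 defines a TEAE by onset date alone, so worsening of an AE already present drops out of the TEAE tables unless sites enter it as a new event

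*SAP*

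**What the plan says.** Table 5 in SAP 3.6.1 has five columns, and each tests one thing.

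- RCP, treatment policy and while-on-treatment: "A TEAE is defined as any AE with onset date on or after the first RCP IP dose". The first closes at the end of the RCP, the second 183 days after the last RCP dose.
- OLP: "A TEAE is defined as any AE with onset date on or after first OLP IP dose".
- Combined RCP and OLP (Any Inebilizumab Analysis Set): the same form, counted from the first inebilizumab dose in either period.
- SFP: "TEAE is defined as any AE with onset date after the last IP dose during the study".

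No column mentions an increase in grade or a change to serious, and the protocol has no TEAE definition of its own.

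Events can exist before dosing. SAP 3.6.1 states "Adverse event and serious adverse event collection begins after the subject signs the informed consent document", and Protocol 8.3 states "All AEs (related and unrelated) will be recorded from written ICF signature up to exit from the study". Protocol 8.2 asks for an onset, a resolution and a severity for each AE, with no instruction to open a new record when severity rises.

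On grade, SAP 3.6.1 says that when the same AE occurs more than once in a subject, "the highest severity and level of relationship observed will be reported". For events that the CTCAE does not list, Protocol 8.1 has the investigator use its own five categories "as defined here, with the maximum severity recorded". SAP 3.1 ends treatment-policy RCP data no later than OLP Day 1.

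**The concern.** The incidence of TEAEs, TESAEs and treatment-emergent AESIs is a secondary endpoint. The SAP's tables of Grade 3 or higher events and of events leading to discontinuation of IP are also built on TEAEs. An event that fails the onset test is absent from all of them, however severe it becomes after dosing.

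The design creates two points at which this can happen. Screening lasts up to 28 days, so AEs can be ongoing at the first RCP dose. Placebo subjects first receive inebilizumab at OLP Day 1, so AEs that began on placebo can be ongoing then. In both cases the worsening, rather than the start, is what follows exposure to the new treatment.

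The SAP provides for carry-over elsewhere. SAP 3.4.4 counts as concomitant a medication started before the first dose and still ongoing at the end of the period. SAP Table 2 resets baseline at the first OLP dose and, for the combined analysis, at the first inebilizumab dose. The AE definition has no equivalent.

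**Working it through.** The point concerns a definition, so there is no figure in the plan to reproduce. The check puts test cases through the Table 5 rules.

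Inputs from the documents: RCP doses on Days 1, 15 and 183 (Week 26); RCP end at Day 365; while-on-treatment end at 183 + 183 = Day 366; OLP Dose 1 within 1 to 38 days after the Week 52 visit (Protocol 6.2.3.1). Assumption: OLP Day 1 falls on Day 380, which is 380 − 365 = 15 days after Day 365 and inside that window. The original onset date is kept when the AE worsens.

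| Case | RCP treatment policy | RCP while-on-treatment | OLP | Combined |
|---|---|---|---|---|
| A. Onset Day −10, worsens Day 30, either arm | no | no | no | no |
| B. Placebo, onset Day 340, worsens OLP Day 20 | TEAE | TEAE | no | no |
| C. Placebo, onset Day 370 (between RCP and OLP), worsens in OLP | no | no | no | no |

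The SFP column does not rescue any of them, since each onset precedes the last IP dose. Case C is a real category: Protocol 6.2.3.1 requires AEs from the interval between the periods to be collected at OLP Visit 1.

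Now let the worsening be entered as a new AE dated at the worsening. In case A, for an inebilizumab subject, onset becomes Day 30: a TEAE in both RCP columns and in Combined. In case B, onset becomes OLP Day 20, or 380 + 19 = Day 399: a TEAE in OLP and Combined. The result therefore turns on a recording convention that neither document states.

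Size. Neither document gives a rate of ongoing AEs at either dose or a rate of worsening. In an RCP arm of 80, one subject newly counted in a row moves it by 1/80 = 1.25 percentage points. The OLP denominators are not known in advance.

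For case B only, purely as an illustration, assume 60 to 78 placebo subjects enter the OLP, with 0.3 to 1.0 ongoing AEs each, of which 5% to 15% worsen. That gives 60 × 0.3 × 0.05 = 0.9 to 78 × 1.0 × 0.15 = 11.7 events. All three inputs are assumed, the range is 13-fold, and it counts any worsening, including Grade 1 to 2. It is not an estimate.

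**The case against.** The strongest reply is that the loss is conditional. Protocol 11.5.1 refers to eCRF Completion Guidelines, which are not part of these documents and could require a worsening to be entered as a new AE. If they do, the onset rule places it in the right period. Protocol 8.1 also excludes from SAEs an elective hospitalization for a pre-existing condition only if that condition did not worsen from baseline, so worsening is not ignored altogether. This stands as a limit on the claim: a reader might infer that such events are always lost, and the documents do not show that. It does not close the gap, because the definition of a secondary safety endpoint should not depend on a convention stated in neither document.

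A second reply is that worsening is visible elsewhere. SAP Table 7 gives worst post-baseline grade and shifts of at least two grades for hematology, chemistry and coagulation, with the baselines of Table 2. SAP 3.6.1 also lists non-treatment-emergent AEs. This largely answers the point for laboratory neutropenia. It does not answer it for arthralgia, an identified risk in Protocol 2.1.4, or for infections, since a listing is not a tabulated incidence.

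A third reply concerns grade. A reader might infer that an AE begun on placebo would appear in the RCP placebo column at the grade later reached on inebilizumab. The text does not support that. The maximum-severity wording in Protocol 8.1 concerns events not listed in the CTCAE, the highest-severity sentence in SAP 3.6.1 concerns repeated occurrences, and SAP 3.1 stops RCP data at OLP Day 1. What remains is narrower: nothing says how a single undated severity would be cut at that day.

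**Conclusion.** The point holds as a gap in the TEAE definition that should be closed. Read as written, and with worsening kept under the original record, Table 5 omits post-dose worsening of screening-onset AEs from every TEAE and TESAE table. It also omits post-crossover worsening of placebo-period AEs from the OLP and Any Inebilizumab tables. The practical exposure is mainly in non-laboratory AEs, and its size cannot be derived from the documents.

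A reader might also infer that the rule systematically makes inebilizumab look safer in the randomized comparison. That is not established. For screening-onset AEs both arms lose events under the same rule, so any excess worsening on drug is concealed, but no direction of bias follows without assuming such an excess. For crossover AEs, the undercount falls in tables that have no concurrent placebo arm.

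**What to change.** Three changes to SAP 3.6.1 and one to site guidance:

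1. In each Table 5 column, keep the onset rule and also count an AE that was present before the first dose of that period and increases in grade or becomes serious on or after that dose. For Combined, the reference is the first inebilizumab dose. The SFP has no dose, so use its Day 1 in Table 2, the day after the last IP dose.
2. Assign to each period only the highest grade reached within it, consistent with the OLP Day 1 cut in SAP 3.1.
3. State one recording convention. Either the AE stays on one record with dated grade changes and the new clause counts it, or a worsening opens a new record, the original is closed, and the onset rule counts it. Applying both would count one worsening twice, which matters most for the rates per 100 person-years because these count events.
4. Put the same convention in the eCRF guidance.

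The cost is SAP wording, a guidance note, and a limited set of queries on the timing of worsening for AEs that span the first RCP dose or OLP Dose 1. Slightly more TEAEs will be counted in both arms. No treatment, visit or efficacy analysis changes.
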